1.3.1.2. Summary of Study GS29735 (ARBAN)

Study Design

ARBAN was a Phase 2, randomized, open-label study designed to evaluate the safety and efficacy of lebrikizumab monotherapy in adult patients (18–75 years of age) with persistent moderate to severe AD, who were inadequately controlled by TCS. A total of 55 patients were randomized to treatment: 28 to lebrikizumab 125 mg Q4W and 27 to TCS.

Efficacy Results

- EASI-50 was achieved by 53.6% and 51.9% of patients in the lebrikizumab and TCS groups, respectively, with a treatment difference of 1.7%. EASI-75 was achieved by 39.3% and 37.0% of patients in the 2 groups, respectively, with a treatment difference of 2.3%.
- Investigator Global Assessment (IGA) scores of 0 or 1 were observed for 7.1% of patients in the lebrikizumab group and 25.9% of patients in the TCS group, giving a treatment difference of –18.8% (95% CI: –37.9%, 0.3%).
- The percent of patients achieving SCORAD-50 or SCORAD-75 showed treatment differences of –19.3% and –7.5%, respectively.

Safety Results

- AEs were reported for a higher proportion of patients in the lebrikizumab group compared with the TCS group (64.3% vs. 37.0%); a higher proportion of patients in the lebrikizumab group, compared with the TCS group, had an AE in the SOC of infections and infestations (42.9% vs. 25.9%). Upper respiratory tract infections were more common in the lebrikizumab group (14.3% vs. 3.7%).
- The overall incidence of skin infection (in the SOC of infections and infestations) was 17.9% in the lebrikizumab group and 7.4% in the placebo/TCS group.
- No serious AEs (SAEs), deaths, anaphylaxis, malignancy, protocol-defined parasitic or targeted intracellular infections of interest, herpes viral infections or zoster, or eosinophilia-associated AEs were reported.

Conclusions

Lebrikizumab was well tolerated at the dose of 125 mg Q4W; the safety profile was generally consistent with previous experience with lebrikizumab in previous trials.

1.3.1.3. Summary of Dose Ranging Study DRM06-AD01

Study Design

DRM06-AD01 was a Phase 2b, randomized, double-blind, placebo-controlled, dose-ranging study to evaluate the safety and efficacy of lebrikizumab in adult patients with moderate to severe AD. 280 patients were randomized to 1 of 4 treatment groups (in a 3:3:3:2 ratio): 73 to lebrikizumab 125 mg Q4W (with a loading dose of 250 mg); 80 to lebrikizumab 250 mg Q4W (with a loading dose of 500 mg); 75 to lebrikizumab 250 mg administered every 2 weeks (Q2W) (with a loading dose of 500 mg given at baseline and Week 2); 52 to placebo Q2W.

Efficacy Results

- Statistically significantly greater proportions of patients in each of the lebrikizumab 250 mg Q4W and 250 mg Q2W groups achieved EASI-50, EASI-75, or EASI-90 at Week 16 than the placebo group.
- A statistically significantly greater proportion of patients in each of the lebrikizumab 250 mg Q4W and 250 mg Q2W groups had both an IGA score of 0 or 1 and a ≥ 2 -point improvement in IGA score at Week 16 than the placebo group.
- The lebrikizumab 250 mg Q2W group had a statistically significantly greater proportion of patients who achieved a ≥ 4 -point improvement in pruritus numerical rating scale (NRS) compared with the placebo group.
- Positive changes in pruritus correlated with positive changes in sleep; the lebrikizumab 250 mg Q4W and 250 mg Q2W groups had statistically significant percent reductions in sleep loss due to itching compared with placebo ($p=0.0459$ and $p=0.0062$, respectively).

Safety Results

- The incidences of conjunctivitis (2.6% all lebrikizumab groups, 0 placebo), herpes infections (2.2% all lebrikizumab groups, 0 placebo), and herpes zoster (0.9% all lebrikizumab groups, 0 placebo) were relatively low.
- Three patients (1.3%) in the lebrikizumab groups and 2 patients (3.8%) in the placebo group had an SAE. Those reported in the lebrikizumab groups were severe chest pain (1 patient in the 250 mg Q2W group), femur fracture of moderate severity (1 patient in the 125 mg Q4W group), and panic attack of moderate severity (1 patient in the 250 mg Q2W group). Those reported in the placebo group were severe chronic obstructive pulmonary disease, severe edema peripheral, and severe pulmonary embolism. All SAEs were considered by the investigator as not related to study drug.
- Most AEs were considered not related to study drug; those considered related were reported for 16.2% of patients in the lebrikizumab groups and 5.8% of patients in the placebo group

Conclusions

This Phase 2b study showed that higher doses of lebrikizumab provided greater clinical benefit. All lebrikizumab doses induced statistically significant reductions in EASI scores compared to placebo, and a good dose response was observed for all primary and key secondary efficacy endpoints. The best response for all endpoints was observed with the highest lebrikizumab dose (250 mg Q2W), although the next highest dose (250 mg Q4W) also induced significant improvement in virtually all endpoints. All doses of lebrikizumab were well tolerated, without a dose response noted; AEs were generally mild or moderate and considered unrelated to study drug. These results provided the basis for dose selection for the pivotal Phase 3 studies.

1.3.1.4. Summary of DRM06-AD03 Phase 1 PK Study

Study Design

DRM06-AD03 was a Phase 1, randomized, parallel-group study to evaluate the pharmacokinetics (PK) and safety of lebrikizumab in healthy adult volunteers (18 to 45 years of age, inclusive). A total of 41 subjects were randomized as follows: 21 subjects received two 1-mL (125 mg) subcutaneous (SC) injections and 20 subjects received one 2-mL (250 mg) SC injection. The primary objective was to compare the PK (AUC, C_{max}) of the 2 lebrikizumab dosing regimens. Blood samples were collected prior to dosing and on Days 2, 4, 6, 8, 11, 15, 29, 43, 57, 71, 85 and 99 for PK and Day 29, 43, 57, 71, 85 and 99 for anti-drug antibodies (ADA).

Pharmacokinetic Results

For each AUC comparison (i.e., AUC_{last} , AUC_{inf} , and AUC_{0-57d}) geometric mean ratios were close to 1 with 90% CIs within the range of 80% to 125%, except for AUC_{inf} , which was just above the upper bound, with a value of 132%. The C_{max} geometric mean ratio was 0.89 with a 90% CI of 73%–108%.

Conclusions

Both the AUC and C_{max} results indicated similar overall exposure between the 2 lebrikizumab dosing regimens evaluated in this study, i.e., two 1-mL (125 mg) SC injections versus one 2-mL (250 mg) SC injection. Data from this study support the use of the 2-mL (250 mg) pre-filled syringe with a pre-assembled needle safety device (PFS-NSD) in the Phase 3 pivotal trials.

1.4. Rationale for Dose and Treatment Regimen

The dosing regimen of 500 mg loading dose at baseline, followed by 250 mg Q2W lebrikizumab was selected for study in this trial, based on an evaluation of safety, efficacy and PK data from the DRM06-AD01 and DRM06-AD03 trials (Section 1.3.1.3 and 1.3.1.4).

The DRM06-AD03 PK study conducted in healthy adults demonstrated that a single SC injection of 2-mL (250 mg) of lebrikizumab delivered comparable levels of lebrikizumab as did two 1-mL (125 mg) SC injections. This simulated the conditions under which study drug will be administered in Phase 3, further supporting the dose and treatment regimen for Phase 3 trials, lebrikizumab 250mg Q2W with a loading dose of 500 mg given at Baseline and Week 2.

Adolescent Patients

In this Phase 3 study, adolescent patients (≥ 12 to < 18 years weighing ≥ 40 kg), will receive 250 mg lebrikizumab (loading dose of 500 mg given at Baseline and Week 2) by subcutaneous injection every 2 weeks (Q2W) which is the same dose of lebrikizumab administered in the adolescent/adult Phase 3 studies. . The justification for this approach is as follows:

Both adults and adolescent patients have similar disease characteristics, typified by prominent Type 2 skin inflammation and similar clinical manifestations. In addition, both groups tend to have similar efficacy outcomes in response to therapies, including dupilumab (Simpson, 2018; Treister, 2019). Pharmacokinetic modeling and simulations of lebrikizumab dosing (population PK modeling of pooled data from 2259 adult asthma patients and a subsequent external posterior predictive check with lebrikizumab PK data from the DRM06-AD01 trial in adult AD patients) revealed similar kinetics for adults and adolescent patients, 12 to < 18 years of age. The maximal exposures are predicted to be slightly ($\leq 35\%$) higher in adolescent patients than in adults for any given dose due to the lower adolescent weight ranges and lebrikizumab exposure dependence on weight; however, the safety profile in adolescent patients, based on the exposure-response relationship analysis and on partial extrapolation, is comparable to that observed in adults.

1.5. Study Conduct Statement

This study will be conducted in accordance with the protocol and with the following:

- Consensus ethical principles derived from international guidelines including the Declaration of Helsinki and Council for International Organizations of Medical Sciences (CIOMS) International Ethical Guidelines
- Applicable ICH Good Clinical Practice (GCP) Guidelines
- Applicable laws and regulations

The protocol, protocol amendments, informed consent form (ICF), Investigator Brochure, and other relevant documents (e.g., advertisements) must be submitted to an independent review committee (IRB)/independent ethics committee (IEC) by the investigator and reviewed and approved by the IRB/IEC before the study is initiated.

Any amendments to the protocol will require IRB/IEC approval before implementation of changes made to the study design, except for changes necessary to eliminate an immediate hazard to study participants.

The investigator will be responsible for the following:

- Providing written summaries of the status of the study to the IRB/IEC annually or more frequently in accordance with the requirements, policies, and procedures established by the IRB/IEC
- Notifying the IRB/IEC of SAEs [and/or UADEs] or other significant safety findings as required by IRB/IEC procedures

- Providing oversight of the conduct of the study at the site and adherence to requirements of 21 Code of Federal Regulations (CFR), ICH guidelines, the IRB/IEC, European regulation 536/2014 for clinical studies (if applicable), and all other applicable local regulations

Investigator sites are compensated for participation in the study as detailed in the clinical trial agreement.

2. STUDY OBJECTIVES AND ENDPOINTS

To evaluate the safety and efficacy of lebrikizumab in adolescent patients (≥ 12 to < 18 years weighing ≥ 40 kg) with moderate-to-severe AD.

2.1. Primary Endpoint

Describe the proportion of patients discontinued from study treatment due to adverse events through the last treatment visit.

2.2. Secondary Endpoints

Over the duration of the study:

- Percentage of patients with an IGA score of 0 or 1 and a reduction ≥ 2 -points from Baseline
- Percentage of patients achieving response of EASI-75 ($\geq 75\%$ reduction from Baseline in EASI score)
- Percentage change from baseline in EASI score and percentage of patients achieving EASI-50 and EASI-90 (≥ 50 and $\geq 90\%$ reduction from Baseline in EASI score, respectively)
- Change from baseline in body surface area (BSA)
- Change from baseline in Patient-Reported Outcomes Information System (PROMIS)[®] Anxiety and Depression measures
- Change from baseline and improvement in Dermatology Life Quality Index (DLQI)/Children's Dermatology Life Quality Index (CDLQI)
- Pharmacokinetics (PK)

3. STUDY DESIGN

This open-label, single arm study is 52 weeks in duration. The study is designed to assess the safety and efficacy of lebrikizumab in adolescent patients with moderate-to-severe atopic dermatitis (Figure 1).

Eligible patients (≥ 12 to < 18 years weighing ≥ 40 kg) will have moderate-to-severe atopic dermatitis for at least one year, defined according to the American Academy of Dermatology Consensus Criteria, have an Eczema Area and Severity Index Score (EASI) of ≥ 16 , an Investigator Global Assessment (IGA) score of ≥ 3 and a body surface area (BSA) of $\geq 10\%$.

Approximately 200 patients will receive 250 mg lebrikizumab (loading doses of 500 mg given at Baseline and Week 2) by subcutaneous (SC) injection every 2 weeks (Q2W). Study drug injections will be administered in the clinic through Week 8 and patients or their caregivers will be instructed on self-administration of the study drug for injections following the Week 8 visit.

Efficacy will be measured using the Investigator's Global Assessment (IGA), Eczema Area and Severity Instrument (EASI) and body surface area (BSA).

Safety will be assessed by monitoring adverse events, serum chemistry, hematology, hormones and urinalysis laboratory testing, physical examination, pulse and blood pressure. An independent Data Safety Monitoring Board will monitor patient safety by conducting formal reviews of accumulated safety data periodically throughout the trial.

Quality of life and impact of disease will be assessed using the Dermatology Life Quality Index (DLQI)/ Children's Dermatology Life Quality Index (CDLQI) and Patient-Reported Outcomes Measurement Information System (PROMIS)[®] Anxiety and Depression measures.

Serum samples will be collected for pharmacokinetic analysis and immunogenicity.

Patients completing this 52-week study will be offered active lebrikizumab treatment in a separate long-term extension study (DRM06-AD07).

Patients who early terminate or choose not to enter the long-term extension study will undergo a safety follow-up visit approximately 12 weeks after the last study drug injection.

A patient is considered to have completed the study if he/she has completed all required phases of the study including the last visit shown in the Schedule of Visits and Procedures. For patients continuing into the long-term extension study, the last study visit is the Week 52 visit. For patients who do not continue into the long-term extension study, the last study visit is the safety follow-up visit, occurring approximately 12 weeks after the last study drug administration.

The end of the study is defined as the date of the last visit of the last patient in the study shown in the Schedule of Visits and Procedures.

Figure 1: Study Schema

3.1. Duration of the Study

The total duration of a patient's participation in this study will be approximately 66 weeks (Screening: maximum duration of 30 days; Treatment Period: 52 weeks; Safety Follow Up: 12 weeks from last dose at Week 50)

3.2. Study Population and Number of Patients

Approximately 200 adolescent patients (≥ 12 to < 18 years, weighing ≥ 40 kg).

4. SELECTION OF PATIENTS

Prospective approval of protocol deviations to recruitment and enrollment criteria, also known as protocol waivers or exemptions, is not permitted.

4.1. Inclusion Criteria

Patients must meet all the following criteria to be eligible for this study:

1. Male or female adolescent (≥ 12 years to < 18 years and weighing ≥ 40 kg).
2. Chronic AD (according to American Academy of Dermatology Consensus Criteria) that has been present for ≥ 1 year before the screening visit (see [Appendix 2](#)).
3. Eczema Area and Severity Index (EASI) score ≥ 16 at the baseline visit.
4. Investigator Global Assessment (IGA) score ≥ 3 (scale of 0 to 4) at the baseline visit.
5. $\geq 10\%$ body surface area (BSA) of AD involvement at the baseline visit.
6. History of inadequate response to treatment with topical medications; or determination that topical treatments are otherwise medically inadvisable.
7. Apply a stable dose of non-medicated, non-prescription moisturizer at least twice daily for ≥ 7 days prior to the baseline visit.
8. Willing and able to comply with all clinic visits and study-related procedures and questionnaires.
9. For women of childbearing potential: agree to remain abstinent (refrain from heterosexual intercourse) or use a highly effective contraceptive method during the treatment period and for at least 18 weeks after the last dose of lebrikizumab.

NOTE: A woman of childbearing potential is defined as a postmenarcheal female, who has not reached a postmenopausal state (≥ 12 continuous months of amenorrhea with no identified cause other than menopause) and has not undergone surgical sterilization (removal of ovaries and/or uterus).

NOTE: The following are highly effective contraceptive methods: combined (estrogen and progestogen containing) hormonal contraception (oral, intravaginal, transdermal) associated with inhibition of ovulation, progestogen-only hormonal contraception (oral, injectable, implantable) associated with inhibition of ovulation, intrauterine device,

intrauterine hormone-releasing system, bilateral tubal occlusion, bilateral tubal ligation, vasectomized partner, or sexual abstinence. The reliability of sexual abstinence should be evaluated in relation to the duration of the clinical trial and the preferred and usual lifestyle of the patient. Periodic abstinence (e.g., calendar, ovulation, symptothermal, or postovulation methods) and withdrawal are not acceptable methods of contraception.

10. Male patients must agree to use an effective barrier method of contraception during the study and for a minimum of 18 weeks following the last dose of study drug if sexually active with a female of child-bearing potential
11. Provide signed informed consent/assent as described in Section 10.2.

4.2. Exclusion Criteria

Patients meeting any of the criteria below will be excluded from this study:

1. Participation in a prior lebrikizumab clinical study.
2. History of anaphylaxis as defined by the Sampson criteria ([Sampson, 2006](#)).
3. Treatment with topical corticosteroids, calcineurin inhibitors or phosphodiesterase-4 inhibitors (e.g., crisaborole) within 1 week prior to the baseline visit.
4. Treatment with any of the following agents within 4 weeks prior to the baseline visit:
 - a. Immunosuppressive/immunomodulating drugs (e.g., systemic corticosteroids, cyclosporine, mycophenolate-mofetil, IFN- γ , Janus kinase inhibitors, azathioprine, methotrexate, etc.)
 - b. Phototherapy and photochemotherapy (PUVA) for AD.
5. Treatment with the following prior to the baseline visit:
 - a. An investigational drug within 8 weeks or within 5 half-lives (if known), whichever is longer.
 - b. Dupilumab within 8 weeks.
 - c. B cell-depleting biologics, including to rituximab, within 6 months.
 - d. Other biologics within 5 half-lives (if known) or 16 weeks, whichever is longer.
6. Use of medicated prescription moisturizers within 7 days of the baseline visit.
7. Regular use (more than 2 visits per week) of a tanning booth/parlor within 4 weeks of the screening visit.
8. Treatment with a live (attenuated) vaccine within 12 weeks of the baseline visit or planned during the study.
9. Uncontrolled chronic disease that might require bursts of oral corticosteroids, e.g., co-morbid severe uncontrolled asthma (history of ≥ 2 asthma exacerbations within the last 12 months requiring systemic [oral and/or parenteral] corticosteroid treatment or hospitalization for > 24 hours).
10. Active chronic or acute infection requiring treatment with systemic antibiotics, antivirals, antiparasitics, antiprotozoals, or antifungals within 2 weeks before the baseline visit, or

superficial skin infections within 1 week before the baseline visit.

NOTE: patients may be rescreened after infection resolves.

11. Evidence of active acute or chronic hepatitis (as defined by the Department of Health & Human Services Centers for Disease Control and Prevention) or known liver cirrhosis.
12. Diagnosed active endoparasitic infections or at high risk of these infections.
13. Known or suspected history of immunosuppression, including history of invasive opportunistic infections (e.g., tuberculosis [TB], histoplasmosis, listeriosis, coccidioidomycosis, pneumocystosis, and aspergillosis) despite infection resolution: or unusually frequent, recurrent, or prolonged infections, per the Investigator's judgment.
14. History of human immunodeficiency virus (HIV) infection or positive HIV serology at screening.
15. In the Investigator's opinion, any clinically significant laboratory results from the chemistry, hematology or urinalysis tests obtained at the screening visit.
16. Presence of skin comorbidities that may interfere with study assessments.
17. History of malignancy, including mycosis fungoides, within 5 years before the screening visit, except completely treated in situ carcinoma of the cervix, completely treated and resolved non-metastatic squamous or basal cell carcinoma of the skin.
18. Severe concomitant illness(es) that in the Investigator's judgment would adversely affect the patient's participation in the study. Any other medical or psychological condition that in the opinion of the Investigator may suggest a new and/or insufficiently understood disease, may present an unreasonable risk to the study patient because of his/her participation in this clinical trial, may make patient's participation unreliable, or may interfere with study assessments.
19. Pregnant or breastfeeding women, or women planning to become pregnant or breastfeed during the study.

5. STUDY DRUG

5.1. Investigational Medicinal Product

Lebrikizumab will be provided to the investigator by the sponsor. Investigational product will be supplied as a solution for subcutaneous injection in a single-use, sterile pre-filled syringe with a pre-assembled needle safety device (PFS-NSD). Each pre-filled syringe is manufactured to contain 250 mg lebrikizumab (2mL injection of 125 mg/mL).

5.2. Storage and Labeling

Study drug is to be stored under refrigerated conditions (2–8°C) and protected from excessive light and heat. Study drug should not be frozen, shaken or stored at room temperature.

Temperature excursions outside of 2–8°C must be reported to the Sponsor or the designee.

Each PFS-NSD will be packaged in a carton and labeled according to the country's regulatory requirements.

5.3. Study Drug Assignment

Patients will be considered enrolled into this study once all Baseline procedures have been completed and the patient has met the inclusion and exclusion criteria. Open-label study drug will be assigned to each patient using an electronic data capture system (an electronic trial supply management system for drug accountability purposes) at each in clinic visit. All patients will receive open label treatment as follows:

- Lebrikizumab 250 mg Q2W: 500mg lebrikizumab administered at Baseline and Week 2 (loading dose) and 250 mg given every two weeks (Q2W) through Week 52.

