I agree to obtain the Institutional Review Board (IRB)/Independent Ethics Committee (IEC) approval of the protocol and informed consent prior to the start of the study.

I agree to obtain formal written informed consent in accordance with applicable federal and local regulations and international guidelines from all patients prior to their entry into the study.

I have received and reviewed the Investigator's Brochure including the potential risks and side effects of the product and instructions for use.

I agree to report to the Sponsor any adverse events that occur during the study in accordance with the ICH GCP guideline and the protocol.

I agree to ensure that all associates, colleagues, and employees assisting me with the conduct of the study are informed of their responsibilities in meeting the above commitments and the commitments set forth in the Investigator's Agreement.

I agree to maintain adequate and accurate records and to make those records available for inspection in accordance with the ICH GCP guideline, and federal and local requirements.

I understand that the study may be terminated, or enrollment suspended at any time by the Sponsor, with or without cause, or by me if it becomes necessary to protect the best interests of the study patients.

Investigator's Signature

Date

Investigator's Name (print)

PROTOCOL SYNOPSIS

Title:	An Open-Label, Single-Arm Study to Assess the Safety and Efficacy of Lebrikizumab in Adolescent Patients with Moderate-to-Severe Atopic Dermatitis
Protocol Number:	DRM06-AD17
Phase:	3
Number of Sites:	Approximately 70 sites in North America, Asia Pacific region and the European Union (EU).
Study Population: Adolescent patients (≥ 12 to < 18 years weighing ≥ 40 kg) with moderate-to-severe atopic dermatitis (AD) who are candidates for systemic therapy.	
Sample Size: 200 patients	
Study Objective: To evaluate the safety and efficacy of lebrikizumab in adolescent patients (≥ 12 to < 18 years weighing ≥ 40 kg) with moderate-to-severe AD.	
Duration of Patient Participation: Screening: Maximum duration of 30 days Treatment Period: 52 weeks Safety Followup: 12 weeks after last dose administered at Week 50 Maximum total participation: 66 weeks	
Study Treatment: Lebrikizumab, 250 mg (2 mL injection of 125 mg/mL)	

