7.16. Week 48 (\pm 5 Days)

- Review and record AEs and update concomitant medication and procedure/therapy information
- Measure vital signs
- Conduct urine pregnancy test (WOCBP only)
- Administer study drug and dispense study drug for next injection

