7.17. Week 52/Early Termination (\pm 5 Days)

- Administer the DLQI/CDLQI and PROMIS anxiety and depression measures
- Complete the following assessments: IGA, BSA, and EASI
- Perform a complete physical examination, including height and weight
- Review and record AEs and update concomitant medication and procedure/therapy information
- Measure vital signs

- Draw pre-dose blood samples for laboratory tests, PK and ADA testing
- Draw blood sample for hormone testing
- Collect a urine sample for urinalysis
- Conduct urine pregnancy test (WOCBP only)

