12. APPENDICES

APPENDIX 1. SCHEDULE OF VISITS AND PROCEDURES

Study Procedure	Screening	Baseline	Treatment														Safety	
	Day (D): Week (W)	D1	W2 ±3d	W4 ±3d	W6 ±3d	W8 ±3d	W12 ±3d	W16 ±3d	W20 ±5d	W24 ±5d	W28 ±5d	W32 ±5d	W36 ±5d	W40 ±5d	W44 ±5d	W48 ±5d	W52/ET ±5d	12W Post ±5d
Visit Window	1	2	3	4	5	6	7	8	9	10	11	12	13	14	15	16	17	18
Visit Number	1	2	3	4	5	6	7	8	9	10	11	12	13	14	15	16	17	18
Informed Consent/Assent	X																	
Inclusion/Exclusion, Med Hx, Demographics	X	X																
Review Immunization Record	X																	
Safety																		
Vital Signs	X	X	X	X	X	X	X	X	X	X	X	X	X	X	X	X	X	X
Physical Exam, Weight/Height	X							X				X					X	
HIV, Hepatitis	X																	
Hematology, Chemistry, Urinalysis	X					X		X				X					X	
Pregnancy Test	Serum	urine		urine		urine	urine	urine	urine	urine	urine	urine	urine	urine	urine	urine	urine	
Hormone Testing ¹	X							X				X					X	
Adverse Events			X	X	X	X	X	X	X	X	X	X	X	X	X	X	X	X
Concomitant Meds & Procedures	X	X	X	X	X	X	X	X	X	X	X	X	X	X	X	X	X	X
Efficacy and Patient Reported Outcomes																		
IGA, BSA, EASI	X	X		X		X		X				X					X	
DLQI/CDLQI ²		X						X				X					X	
PROMIS Anxiety & Depression ²		X						X				X					X	
Pharmacokinetics (PK) and Immunogenicity (ADA)																		
Pre-dose PK		X		X				X				X					X	X
Pre-dose ADA ³		X		X				X				X					X	X
Study Drug																		
Administer Study Drug		X	X	X	X	X	X	X	X	X	X	X	X	X	X	X	X	
Instruction on Self-Administration						X												
Dispense Drug for At-Home Injection						X	X	X	X	X	X	X	X	X	X	X		

¹ Collect estradiol for females only. Collect testosterone for males only ² Patient reported outcome and quality of life measures should all be completed prior to other study assessments; ³ nAB testing conducted for positive treatment-emergent ADA responses. Additional immunogenicity sample collected for any patient experiencing a hypersensitivity reaction during study.

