6.1. Summary of Study Design

Study J2T-DM-KGAE (KGAE) (also known as DRM06-AD17) is an open-label, single-arm study to assess the safety and efficacy of lebrikizumab in adolescent patients with moderate-to-severe AD. A sample size of approximately 200 adolescent patients (≥ 12 to < 18 years, weighing ≥ 40 kg) is planned.

The study is composed of a 52-week treatment period, with the last study drug injection at Week 50. Patients completing this 52-week study will be offered active lebrikizumab treatment in a separate long-term extension study, J2T-DM-KGAA (DRM06-AD07). Patients who early terminate or choose not to enter the long-term extension study will undergo a safety follow-up visit approximately 12 weeks after the last study drug injection.

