6.1.1. Screening

Screening Period: Patients will be evaluated for study eligibility before the baseline visit (Day 1).

6.1.2. Baseline and Week 2

Patients who meet eligibility criteria are assigned to receive 250-mg lebrikizumab Q2W. At the baseline and Week 2 clinic visits, all patients will be administered a loading dose of 500-mg lebrikizumab as two 2-mL, 250-mg (125-mg/mL) prefilled syringes with a preassembled needle safety device.

6.1.3. Week 4 to Week 52

Patients will return to the clinic at Weeks 4, 6, 8, and every 4 weeks thereafter through Week 52 for safety and efficacy assessments. For Weeks 4 through 50, all patients will be administered one 250 mg lebrikizumab syringe, Q2W. Study drug injections will be administered in the clinic through Week 8 and patients or their caregivers will be instructed on self-administration of the study drug for injections following the Week 8 visit. The clinic visit at Week 52 is the end of the treatment period. Patients completing this 52-week study will be offered active lebrikizumab treatment in a separate long-term extension study (DRM06-AD07/J2T-DM-KGAA).

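### Protocol 5.3 and Appendix 1 place a dose at Week 52, while the Synopsis, Protocol 3.1 and SAP 6.1 and 6.1.3 end dosing at Week 50

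*Protocol*

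**What the plan says.** **A dose at Week 52.** Protocol 5.3, the study drug assignment section, sets the regimen after the loading doses as "250 mg given every two weeks (Q2W) through Week 52". In Appendix 1 the row "Administer Study Drug" is marked at every visit from Baseline to the shared W52/ET column, 16 marks in all.

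**Last dose at Week 50.** Four places say so:
- Protocol Synopsis: "12 weeks after last dose administered at Week 50".
- Protocol 3.1: "Safety Follow Up: 12 weeks from last dose at Week 50".
- SAP 6.1: "The study is composed of a 52-week treatment period, with the last study drug injection at Week 50".
- SAP 6.1.3: "For Weeks 4 through 50, all patients will be administered one 250 mg lebrikizumab syringe, Q2W".

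**Passages that do not settle it.** Protocol 7.17 (Week 52/Early Termination) lists no administration step, whereas each visit list from Baseline to Week 48 has one; Week 48, for instance, reads "Administer study drug and dispense study drug for next injection". Yet 7.17 also tells the site to "Draw pre-dose blood samples for laboratory tests, PK and ADA testing". Protocol 5.4 speaks in general terms of in-clinic dosing at all scheduled visits after Week 8.

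**The concern.** Week 52 lies on the two-week grid that starts at Baseline, so dosing through Week 52 and a last dose at Week 50 are different schedules. The choice decides whether an adolescent receives an injection at the Week 52 visit. It also fixes the calendar position of periods counted from the last dose: the 12-week safety follow-up (Protocol 7.18) and the 18-week contraception periods for females and males (Protocol 4.1, criteria 9 and 10). The expected number of injections behind the 75% compliance rule (Protocol 9.6, SAP 7.8) depends on it as well.

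A related layout problem sits in the same table cell. The W52/ET column serves both visits, so its dosing mark also covers the early-termination visit. Protocol 8.6.2 requires that visit of patients who have permanently stopped study drug. This is a conflict in the table, not an instruction to dose them.

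**Working it through.** **1. The plan's own participation figure.** The Synopsis and Protocol 3.1 give 66 weeks, with screening of at most 30 days and follow-up 12 weeks after the last dose. Total = 30/7 + last dosing week + 12.
- Last dose Week 50: 4.29 + 50 + 12 = 66.29 weeks, which reproduces 66.
- Last dose Week 52: 4.29 + 52 + 12 = 68.29 weeks, which does not.

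This is not independent evidence for Week 50, because the 66 stands in the same statements that name Week 50.

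**2. Dosing occasions.**
- Visit lists 7.2 to 7.16 with an administration step: Weeks 0, 2, 4, 6, 8, then 12 to 48 every 4 weeks = 5 + 10 = 15.
- Home doses from the 11 dispensing marks in Appendix 1 (Week 8 to Week 48): Weeks 10, 14, ..., 50 = 11.
- Visit lists plus home doses: 15 + 11 = 26, that is Weeks 0, 2, ..., 50.
- Appendix 1 dosing row plus home doses: 16 + 11 = 27, that is Weeks 0, 2, ..., 52.

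The dosing row lines up with the fully marked vital-signs row, with blanks at screening and at the follow-up visit. The dispensing row stops at Week 48. The W52/ET dosing mark is therefore not a shifted column.

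**3. Syringes and dose.** Each of the two loading doses uses one extra 250 mg syringe.

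| | Last dose Week 50 | Last dose Week 52 |
|---|---|---|
| Dosing occasions | 26 | 27 |
| Syringes | 26 + 2 = 28 | 27 + 2 = 29 |
| Total dose | 28 × 250 = 7,000 mg | 29 × 250 = 7,250 mg |
| Follow-up visit | 50 + 12 = Week 62 | 52 + 12 = Week 64 |
| End of contraception period | 50 + 18 = Week 68 | 52 + 18 = Week 70 |

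The last two rows apply to completers who do not enter DRM06-AD07. Those who enter it finish this study at Week 52 and are offered further lebrikizumab. Early terminators count from their own last injection.

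**4. Compliance cut-off (at least 75% of expected).**
- By syringes (SAP 7.8): 0.75 × 28 = 21.0, so 21 are needed; 0.75 × 29 = 21.75, so 22 are needed. A patient with 21 has 21/28 = 75.0% or 21/29 = 72.4%.
- By full sets (Protocol 9.6): 0.75 × 26 = 19.5, so 20 are needed; 0.75 × 27 = 20.25, so 21 are needed. A patient with 20 has 20/26 = 76.9% or 20/27 = 74.1%.
- If the Week 52 dose is both expected and given, that patient has 22/29 = 75.9% by syringes and stays compliant.

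**5. The ambiguous passages.** The pre-dose wording in 7.17 proves nothing, because Appendix 1 puts the same label on the 12-week follow-up sample, when no dose is due. Protocol 5.4, read literally, would also reach the follow-up visit, so it is weak support for a Week 52 dose. What remains of 7.17 is the missing administration step, which contradicts the Appendix 1 mark within the protocol itself.

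**The case against.** The strongest reply is that this is a slip with an obvious reading. The wording in 5.3 can be taken loosely as the end of the 52-week treatment period. Appendix 1 also departs from the visit lists elsewhere: it marks vital signs at the 12-week follow-up, which 7.18 does not list, so a stray mark is plausible. Four explicit statements and the missing step in 7.17 then stand against one phrase and one table cell. Drug is assigned through an electronic system at each clinic visit, which may already settle the matter. The periods counted from the last dose adjust themselves once the last dose is known. SAP 7.8 allows the expected number to come from the dispense dataset, so a dose never dispensed need not enter the denominator.

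Much of this stands. The Week 50 passages are more numerous, the system's Week 52 setting is not visible, and it is not shown that sites would act differently. The follow-up and contraception shifts are consequences of the conflict, not separate faults. The compliance effect is marginal. But the loose reading of 5.3 does not explain the Appendix 1 mark, and Protocol 7 sends the reader to Appendix 1 for the required procedures at each visit. A stray mark is a guess that the text does not confirm, and none of these passages is superseded text.

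**Conclusion.** The inconsistency is real and should be fixed. It concerns one injection of 250 mg at one visit per completer, and a two-week shift in the follow-up visit and the end of contraception for completers who do not roll over; the documents do not show how many that will be.

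The statistical effect is small. The primary endpoint definition does not change, exposure duration runs to the last visit of the treatment period, and total dose uses injections actually taken (SAP 7.13.1). Compliance status changes only for a completer exactly at the margin, and only if a Week 52 dose is counted as expected but not given. SAP 7.15 names compliance below 75% as a possible important deviation, so such a patient would be affected there too.

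The counts assume full dosing on the nominal two-week grid, with one extra syringe at Baseline and at Week 2. Which schedule is intended is for the sponsor and is not judged here.

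**What to change.** State once whether study drug is given at the Week 52 visit, and bring Protocol 5.3, 5.4, 7.17, Appendix 1, the Synopsis, Protocol 3.1 and SAP 6.1 and 6.1.3 into line with that decision. Align the participation figure and the expected number of injections with the result. Make the shared W52/ET dosing mark consistent with 7.17 and 8.6.2, for example by a footnote that separates the two visits.

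In the same pass, correct the references in Protocol 8.6.1 and 8.6.2 that send the reader to Section 7.18 for the early-termination visit: 7.18 is the Safety Follow-up Visit, and the early-termination list is in 7.17.

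The cost is a protocol clarification, one table mark or footnote and two cross-references, plus matching SAP wording if the decision requires it. No new data or patients are needed.
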